## **4.7 Lost to Follow-up**

The following actions must be taken if a participant fails to return to the clinic for a required study visit and/or is unable to be reached for follow-up:

- The investigator or designee must make every effort to regain contact and/or reschedule a missed visit with the participant.
- A participant is deemed lost to follow-up if his/her status cannot be obtained after *all* of the following occurs at two consecutive scheduled protocol calendar timepoints:
  - Three telephone calls (at least one day apart) from the study team are unanswered  
**AND**
  - A letter to the participant's last known mailing address goes unanswered (refer to Appendix 2).  
**AND**
  - These contact attempts must be documented in the participant's medical record or study file.
- Update OnCore® (follow-up tab and eCRF) when a participant is officially considered lost to follow-up.
- If a subject is considered lost to follow-up, but subsequently contacts the participating site study team, the subject should be considered in follow-up again.

#### **4.8 Accrual Suspension and Closure**

The MCW PI facilitates the suspension and closing of accrual in the following manner:

- OnCore® tracks accrual throughout the study.
- If the study must be suspended, OnCore® is updated to a “suspended” status.
- When the accrual number is reached, OnCore® notifies staff of study closure.

#### **4.9 End of Study Definition**

A participant is considered to have completed the study if he or she has completed all phases of the study including the last visit or the last scheduled procedure shown in the calendar of events or has been discontinued.

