Study Intervention Description	Enrolled patients will receive SRS to all metastases followed by surgical resection of resectable metastases within one to 10 days following

	SRS. Pathologic specimens will be analyzed, and the patient will enter a standard pattern of surveillance (brain MRI every three months for two years).
Number of Subjects	Up to fifteen subjects will be enrolled in this study to attain ten completed subjects.
Estimated Time to Complete Enrollment:	Approximately two years.

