# **3 STUDY DESIGN**

## **3.1 General Description**

This is a single-arm, single-center, pilot study in which 10 completed patients with one to four brain metastases diagnosed on brain MRI within the past 30 days will be evaluated for study eligibility and enrolled as appropriate.

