## **4.6 Discontinuation of Study Treatment, Withdrawal, and Compliance**

Discontinuation from the study treatment does not mean discontinuation from the study. Subject will be considered in follow-up; study procedures should still be completed as indicated by the study protocol and AEs/SAEs will continue to be reported according to this protocol.

In the absence of treatment delays due to adverse events, study treatment/intervention may continue until:

- Disease progression.
- General or specific changes in the subject's condition renders the subject unacceptable for further treatment in the investigator's judgment.
- Intercurrent illness that prevents further treatment administration.
- Subject decides to withdraw from the study.
- The subject has significant noncompliance with the protocol (see below).
- Unacceptable adverse event(s) and/or dose level reduction beyond requirements as detailed in this protocol.
- Study stopping rules are met.

Subjects who sign the informed consent form, and are enrolled and receive the study intervention, but subsequently withdraw, or are withdrawn or discontinued from the study will not be replaced.

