## **7.3 Missing data and interim stopping**

If patients do not complete the follow-up period, patients will be considered lost to attrition and their data will not be used for the primary or secondary objectives, except possibly for demographic descriptions. No missing data imputation or specific analysis is planned for this study. Since the primary objectives of this study are to study feasibility rather than evaluate efficacy or futility – early stopping is not meaningful in the present context. No stopping rules or interim evaluations are planned for this study.

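### The target of 10 completed subjects does not match the analysis set, so the rules guarantee no minimum number of patients analysed

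*Combined protocol and SAP*

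**What the plan says.** The summary gives the target as "Up to fifteen subjects will be enrolled in this study to attain ten completed subjects", and section 3.1 describes a "single-arm, single-center, pilot study in which 10 completed patients with one to four brain metastases". Four sections bear on how that target works:

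- Section 4.9 is the only place that says what completing the study means. Besides finishing all phases, its definition takes in "or the last scheduled procedure shown in the calendar of events or has been discontinued".
- Section 4.6 says that subjects who are enrolled and receive the intervention "but subsequently withdraw, or are withdrawn or discontinued from the study will not be replaced".
- Section 7.3 says of those who do not finish follow-up that "patients will be considered lost to attrition and their data will not be used for the primary or secondary objectives", with a possible exception for demographic description.
- Section 4.8 says "When the accrual number is reached, OnCore® notifies staff of study closure" and does not give the number.

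Section 7.1 rests its precision statement on about 10 patients and an 85% local control rate, with a 95% interval no wider than 0.40. Section 7.2 names the exact binomial method. Section 2.3 takes enrolled subjects as the feasibility denominator.

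**The concern.** Recruitment is steered by one count and the analysis uses another. A subject who is treated and then leaves the study can fill one of the 10 places and contribute nothing to the local control estimate, with nobody recruited instead. No section sets a lower limit on the number analysed.

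Taking *completed* to mean finishing follow-up does not rescue the plan. The study calendar runs follow-up for 18 months from a visit held one month after radiosurgery, so completion is known only about 19 months after treatment. Enrolment is expected to take about two years (section 3.3), so there is no workable moment at which to decide on patients 11 to 15. Section 3.2 adds a second follow-up length, MRI surveillance for two years.

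Precision is not the only thing at stake. Section 7.3 discards local control data already observed in patients who later leave. Section 4.6 lists disease progression among the reasons for investigator withdrawal, so the exclusion could remove failures and flatter the control rate. This is a possibility, not a certainty, because footnote 2 of the study calendar keeps progressed and withdrawn subjects in follow-up.

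**Working it through.** **The rules applied to one subject, treated and then discontinued from the study**

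| Question | Section | Answer |
|---|---|---|
| Completed? | 4.9 | Yes |
| Replaced? | 4.6 | No |
| Analysed for primary and secondary objectives? | 7.3 | No, if follow-up is unfinished |
| Does accrual close at 10 completed or 15 enrolled? | 4.8 | Not stated |

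**The plan's own figure.** 0.40/0.85 = 0.471, so the stated 47% is right. The width is not reproduced by the planned method. With k controlled of n, the Clopper-Pearson limits are the 0.025 quantile of Beta(k, n−k+1) and the 0.975 quantile of Beta(k+1, n−k). At n = 10 the widths are 0.531 for 8/10, 0.442 for 9/10 and 0.308 for 10/10.

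**Width against the number analysed.** Expected width = Σ P(K = k) × width(k, n), with K ~ Binomial(n, 0.85). The narrowest interval occurs when all n are controlled and equals 1 − 0.025^(1/n).

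| n analysed | Expected width | Narrowest possible |
|---|---|---|
| 15 | 0.385 | 0.218 |
| 10 | 0.468 | 0.308 |
| 8 | 0.520 | 0.369 |
| 7 | 0.553 | 0.410 |
| 5 | 0.642 | 0.522 |
| 4 | 0.703 | 0.602 |

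With 7 or fewer analysed, no result can meet 0.40.

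**How many might remain.** The documents give no attrition rate and do not say whether death counts as not finishing follow-up. Assume that it does and that survival is exponential, S(t) = 2^(−t/median). Eligibility requires an estimated median of at least six months; the rest of the range is assumed.

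| Median (months) | S(18) | S(19) | Left of 10 at 19 months | Left of 15 at 19 months |
|---|---|---|---|---|
| 6 | 0.125 | 0.111 | 1.1 | 1.7 |
| 12 | 0.354 | 0.334 | 3.3 | 5.0 |
| 18 | 0.500 | 0.481 | 4.8 | 7.2 |
| 24 | 0.595 | 0.578 | 5.8 | 8.7 |

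**If *completed* meant analysable under section 7.3.** Fifteen enrolled give 10 on average only if attrition is at most 1 − 10/15 = 33%. The binomial probability of at least 10 analysable of 15 is 0.94, 0.72, 0.40 and 0.15 at assumed attrition of 20%, 30%, 40% and 50%.

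**The case against.** A reader might infer more than the text supports, in four ways.

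*Three rival definitions of completion.* Only section 4.9 defines it, under an end-of-study heading, and nothing ties that definition expressly to the accrual target. Section 4.6 is a replacement rule and section 7.3 an analysis-set rule. *Discontinued* in section 4.9 is also ambiguous, since section 4.6 separates stopping treatment from leaving the study. What stands is that the rules do not fit together for a subject who leaves the study early.

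*A flat contradiction between section 4.6 and the up-to-15 rule.* Section 4.6 bars replacement only of treated subjects. The five extra places could cover those enrolled but never treated. That reading is consistent, but the protocol does not state it.

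*Accrual stopping at 10.* This is permitted, not required. Suppose 15 patients enrol evenly over 24 months and deaths count as discontinued. The number completed under section 4.9 at month 24 is then 15 × [1 − (m/(24 ln 2)) × (1 − 2^(−19/m))] for median m, which is 10.2, 7.8 and 6.6 at medians of 6, 12 and 18 months. In two of these three cases the cap is reached first. The analysed number still falls short of 10, as the last column of the survival table shows.

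*The whole gap to 0.40 as the effect of this mismatch.* At n = 10 the expected width is already 0.468, and P(width ≤ 0.40) is about 0.85^10 = 0.20. That is a separate point about section 7.1. The part that belongs here is the rise from 0.468.

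It is also fair to say that most of the loss comes from section 7.3. At a 12-month median, running accrual to 15 but leaving section 7.3 alone moves the expected number analysed only from 3.3 to 5.0.

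**Conclusion.** The concern holds as a mismatch between the accrual target and the analysis set. As written, the closing point for enrolment cannot be determined, and the analysed number has no lower bound although section 7.1 assumes about 10. This follows from the text alone.

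The size does not. It rests on assumed exponential survival, on assumed medians of 6 to 24 months, and on counting death as not finishing follow-up. Six months is an eligibility floor for each patient's estimate and so an extreme value for the whole cohort. Under those assumptions about 1 to 6 of 10, or 2 to 9 of 15, remain at 18 to 19 months. A fall from 10 to 7 analysed adds 0.085 to the expected width (0.553 − 0.468), and a fall to 5 adds 0.174 (0.642 − 0.468). The documents do not establish that a shortfall of any particular size will occur.

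**What to change.** 1. For accrual, define *completed* by an early observable event: SRS plus the protocol resection. Do not use the section 4.9 wording for this purpose. State the closing number in section 4.8, together with the cap of 15.
2. State in section 4.6 which subjects the five extra places cover, so that it agrees with the up-to-15 rule.
3. Replace the section 7.3 exclusion. Keep every enrolled subject in the feasibility denominator. Analyse local control in one named set, for example all SRS-treated patients with those not resected reported separately, using all observed follow-up. The method can be a time-to-event estimate with censoring, cumulative incidence with death as a competing event, or an exact binomial proportion at a fixed time with a stated rule for patients not assessable then. Section 7.2 must change to match, because a simple exact binomial proportion cannot use censored data.
4. Restate the section 7.1 precision for that set and method.

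The cost is revised wording in the summary and sections 4.6, 4.8, 4.9, 7.1, 7.2 and 7.3, a little more analysis work, and a less favourable stated precision. No patients are needed beyond the cap of 15. If accrual closes once 10 have been resected, the number enrolled depends on the feasibility numerator, so both counts and the stopping rule should be reported.

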#### **4.10 Study Discontinuation and Closure**

This study may be temporarily suspended or prematurely terminated if there is sufficient reasonable cause (as determined by the MCW study principal investigator, DSMC, sponsor, and/or IRB). Written notification, documenting the reason for study suspension or termination, will be provided by the suspending or terminating party to study participants, investigator, funding agency, and regulatory authorities. If the study is prematurely terminated or suspended, the MCW principal investigator (PI) will promptly inform the MCW Institutional Review Board (IRB) and sponsor and will provide the reason(s) for the termination or suspension. Study participants will be contacted, as applicable, and be informed of changes.

## 5 TREATMENT PLAN

### 5.1 Intervention Description

Guidelines for treatment based on tumor diameter (in cm)	
Maximum Tumor Diameter	Prescribed Dose
≤ 2 cm	20–24 Gy
2.1–3.0 cm	18 Gy
3.1–5.0 cm	15 Gy

SRS followed by surgery within one to 10 days.

- A typical SRS dose of 20 Gy applied to one to four brain metastases provides local control of approximately 90%.
- 15 Gy to 18 Gy = threefold increase in local failure compared to 24 Gy.

#### 5.1.1 Stereotactic Radiosurgery

SRS will be delivered utilizing Gamma Knife®. Target volume and isocenter determination will be based on a brain MRI with the patient's head in the stereotactic frame or face mask. SRS will be delivered to each lesion that has not previously undergone treatment. Due to the volumetric summation constraint for the remaining metastases, no single, non-resected lesion greater than 5 cm will be allowed in the study.

If any two lesions are within 0.8 to 2 cm of each other, the intervening midplane dose will not exceed 15 Gy. This may require treating each respective target with a lesser dose than dictated by the above dosing criteria to minimize toxicity. The dose to the critical structures, including optic pathway, brainstem, cochlea, and medulla, must meet constraints as determined by the radiation oncologist. If the above constraints cannot be met utilizing the prescribed radiosurgery dose, then the highest dose to the target volume will be used such that constraints can be met. This will be considered a minor deviation.

#### Possible Side Effects Related to Stereotactic Radiosurgery (SRS)

##### Common, Some May Be Serious

In 100 people receiving SRS, more than 20 and up to 100 may have:

Temporary (short-term) pain from with the head frame placement (if a head frame is used).

##### Occasional, Some May Be Serious

In 100 people receiving SRS, from four to 20 may have:

- Headache
- Localized hair loss which may be permanent
- Nausea

- Vomiting
- Allergic reaction to the local anesthesia (rash, itching, nausea, or difficulty breathing)
- Bleeding and/or infection around the head frame (if a head frame is used)
- Swelling of the brain in the treated area which may require treatment with steroids
- Severe local damage to or death of normal brain tissue, which may require surgery to remove

#### **Rare and Serious**

- In 100 people receiving SRS, three or fewer may have:
- Decreased brain function such as motor function (coordination/movement)
- Hardening of the arteries in the brain which rarely may lead to strokes many years after stereotactic radiosurgery
- A second new cancer caused by radiation, in the brain or nearby organs which rarely may occur many years after stereotactic radiosurgery
- Damage to vision tracts (eye damage) with the possibility of permanent blindness

Long-term effects of the radiation or radiosurgery used in this study include an increased risk of developing other cancers.

#### **5.1.2 Surgical Resection**

At least one of the four lesions must be either larger than 3 cm or symptomatic to meet the surgical resection criteria. One to 10 days after radiosurgery, the dominant lesion(s) will be maximally resected and labeled tissue will be sent to the neuropathology department for clinical diagnosis and radiobiological correlative studies. If for safety concern or other considerations, gross total resection is not reached, the residual disease in the setting of subtotal resection will be closely observed given that it has been treated with a definitive dose of SRS, reserving salvage local therapy for cases of progression.

#### **Possible Side Effects Related to Surgical Resection**

##### **Common, Some May Be Serious**

In 100 people receiving neurosurgery 20 to up to 90 patients may have:

- Pain
- Headache
- Nausea
- Vomiting

##### **Occasional, Some May Be Serious**

In 100 people receiving neurosurgery, 15 to up to 20 patients may have:

- Bleeding
- Infection

#### **Rare and Serious**

In 100 people receiving neurosurgery, less than five patients may have:

- Stroke
- Permanent injury, i.e., arms and legs not functioning properly, issues with speech
- Complications from anesthesia, i.e., heart or lung problems

## 6 ADVERSE EVENTS: DEFINITIONS, COLLECTION AND REPORTING REQUIREMENTS

### 6.1 Definitions

#### 6.1.1 Adverse Event

Any untoward medical occurrence in a patient or clinical investigation subject administered a pharmaceutical product and which does not necessarily have to have a causal relationship with this treatment. (International Conference on Harmonisation [ICH], E2A, E6).

This study will utilize the NCI Common Terminology Criteria for Adverse Events (CTCAE) version 5.0, located on the CTEP web site:

[https://ctep.cancer.gov/protocolDevelopment/electronic\\_applications/ctc.htm](https://ctep.cancer.gov/protocolDevelopment/electronic_applications/ctc.htm)

AEs may be spontaneously reported by the patient and/or in response to an open question from study personnel or revealed by observation, physical examination or other diagnostic procedures.

#### 6.1.2 Serious Adverse Event (SAE)

Serious Adverse Event (SAE) means any untoward medical occurrence that results in any of the following outcomes:

- **Death.** Results in death.
- **Life-threatening.** Is life-threatening (refers to an AE in which the patient was at risk of death at the time of the event. It does not refer to an event which hypothetically might have caused death if it were more severe).
- **Hospitalization.** Requires inpatient hospitalization or prolongation of an existing hospitalization (see clarification in the paragraph below on planned hospitalizations).
- **Disability/incapacity.** Results in persistent or significant disability or incapacity. (Disability is defined as a substantial disruption of a person's ability to conduct normal life functions).
- **Pregnancy**
- **Medically important event.** This refers to an AE that may not result in death, be immediately life threatening, or require hospitalization, but may be considered serious when, based on appropriate medical judgment, may jeopardize the patient, require medical or surgical intervention to prevent one of the outcomes listed above, or involves suspected transmission via a medicinal product of an infectious agent. Examples of such medical events include allergic bronchospasm requiring intensive treatment in an emergency room or at home, blood dyscrasias or convulsions that do not result in inpatient hospitalization, or the development of drug dependency or drug abuse; any organism, virus, or infectious particle (e.g., prion protein transmitting transmissible spongiform encephalopathy), pathogenic or nonpathogenic, is considered an infectious agent.

### **6.1.3 Attribution of an Adverse Event**

An assessment of the relationship between the adverse event and the medical intervention, using the following categories:

**Definitely Related:** *The AE is clearly related to the intervention.* There is clear evidence to suggest a causal relationship, and other possible contributing factors can be ruled out.

**Probably Related:** *The AE is likely related to the intervention.* There is evidence to suggest a causal relationship, and the influence of other factors is unlikely.

**Possibly Related:** *The AE may be related to the intervention.* There is some evidence to suggest a causal relationship (e.g., the event occurred within a reasonable time after administration of the trial medication). However, the influence of other factors may have contributed to the event (e.g., the subject's clinical condition, other concomitant events).

**Unlikely:** *The AE is doubtfully related to the intervention.* A clinical event, including an abnormal laboratory test result, whose temporal relationship to drug administration makes a causal relationship improbable (e.g., the event did not occur within a reasonable time after administration of the trial medication) and in which other drugs or chemicals or underlying disease provides plausible explanations (e.g., the subject's clinical condition, other concomitant treatments).

**Unrelated:** *The AE is clearly NOT related to the intervention.* The AE is completely independent of study drug administration, and/or evidence exists that the event is definitely related to another etiology.

### **6.1.4 Expectedness of an Adverse Event**

Study investigator or treating physician will be responsible for determining whether an AE is expected or unexpected as indicated in the protocol, informed consent form and/or drug information brochure. An AE will be considered unexpected if the nature, severity, or frequency of the event is NOT consistent with the risk information previously described for the study intervention.

## **6.2 Collection and Reporting Requirements for Adverse Events and Serious Adverse Events**

### **6.2.1 Collection of Adverse Events**

All grade 3, 4, and 5 adverse events (including all SAEs) must be recorded in OnCore® and/or an adverse event log. All AEs required to be collected must be graded according to the CTCAE v5. When possible, signs and symptoms indicating a common underlying pathology should be noted as one comprehensive event. Investigator's or treating physician's assessment of AE attributions must also be documented.

AEs will be collected from the time the subject signs the consent form through 30 days post last dose of study drug(s). AEs will be tracked and followed until resolution, subject withdraws consent, or is lost to follow-up (including subjects who discontinue early). All adverse events collected per the protocol will be followed with appropriate medical management until they are resolved, if they are related to the study treatment, or until the investigator deems the event to be chronic.

Please see section 6.2.2 and table 2 to identify the adverse events that need to be reported.

### 6.2.2 Reporting of Adverse Events and Serious Adverse Events

Please refer to table 2 below to identify adverse events that meet reporting requirements.

All serious adverse events (SAEs) that occur after the subject has signed the consent form through 30 days post last dose of study drug(s) will be reported. All SAEs will be followed until satisfactory resolution, or until the investigator deems the event to be chronic.

All serious adverse events (SAEs) must also be documented in OnCore®.

